## **1 INTRODUCTION**

This document is a clinical investigational plan for a human research study sponsored by Masimo Corporation. The study will be conducted in accordance with the ethical principles that have their origin in the Declaration of Helsinki. By participating in the study, the Investigator agrees to adhere to all stipulations of this protocol, the conditions of IRB approval, federal and local regulatory requirements, 21 CFR 812, ISO-14155 and International Conference on Harmonization Good Clinical Practice (ICH GCP) guidance.

### **1.1 Background and Rationale**

Hemoglobin (Hb) is a protein contained in the red blood cells that is responsible for carrying oxygen from the lungs to tissues throughout the body. The concentration of hemoglobin in whole blood is expressed in grams per deciliter (g/dL). Normal Hb range for adult males is 13 to 18 g/dL and 12 to 16 g/dL for adult females. Sufficient hemoglobin level must be maintained to ensure adequate tissue oxygenation; a person with low levels of hemoglobin is referred to as anemic. Some common causes of anemia are:

- Nutritional deficiency - iron, vitamin B12 and folate
- Abnormal hemoglobin structure - sickle cell or thalassemia
- Acute loss of blood due to traumatic injury or surgical procedure
- Chronic diseases - cancer, kidney and liver failure

If left untreated, anemia can cause several complications, such as:

- Fatigue
- Heart problems, such as arrhythmia
- Death in the case of acute blood loss

To assess a patient's anemia status, a physician would typically request a complete blood count (CBC) test to evaluate hemoglobin levels. The National Committee for Clinical Standards (NCCLS) has published an approved gold standard procedure for the manual measurement of hemoglobin using the cyanmethemoglobin method (HiCN). This method breaks down red blood cells to get the hemoglobin into a solution. Then, the free hemoglobin is oxidized to form methemoglobin and combined with cyanide ions, resulting in cyanmethemoglobin. The concentration of hemoglobin is then determined by shining a light through the solution and measuring how much light is absorbed- specifically at a wavelength of 540 nanometers. Manual HiCN has gradually been phased-out of mainstream laboratory use, because it is time and labor intensive and exposes the operator to harmful reagents. Instead, there are automated analyzers based on the same operating principle of HiCN that are more widely used, such as Beckman Coulter and Advia 120, and Sysmex hematology analyzers. However, HiCN still remains that reference method that all automated analyzers are compared against.

[figure not shown]
These routine CBC tests are invasive, intermittent, increase infection risk to patient, and can expose a clinician to the risk of infection via blood borne pathogens. In addition, multiple blood tests at hospitals have been attributed to patients developing hospital acquired anemia (HAA). A recent study looked at more 17000 myocardial infarction patients across 57 US hospitals and found 20% of the patients had developed HAA over their hospital stay.

Recent advancements in pulse oximetry technology have led to the development and FDA-approval of a multi-wavelength Pulse CO-Oximeter, designed for continuous, noninvasive measurement of total hemoglobin concentration (Masimo SpHb™ technology). Thus, noninvasive measurement of total hemoglobin fortify a clinician's toolkit and can potentially offer a great clinical value and provide a simple, portable, safe and accurate method for monitoring patients.

[figure not shown]
To evaluate the accuracy of hemoglobin measurement, data collection and analysis of blood should be conducted in a controlled manner to reduce variability between noninvasive hemoglobin readings to the hemoglobin value obtained from a reference sample. Small differences in the processing and/or handling of hemoglobin may have dramatic effects in analytical reliability and reproducibility. Therefore, potential bias and confounding factors should be minimized as much as possible by having consistent technique of clinician, posture of the donor, timing of samples, etc.

## 1.2 Investigational Devices

SpHb technology uses a multiwavelength sensor with various light emitting diodes (LEDs) that pass light through the measurement site to a photodiode (detector) as shown in **Figure 1** below. Signal data is obtained by passing various [REDACTED] wavelengths [REDACTED] through a capillary bed (for example fingertip) and measuring changes in absorption during the blood pulsatile cycle. The detector receives the light and converts it to an electrical signal which is, in turn, used to predict SpHb.

**Figure 1:** SpHb Technology Overview

**Figure 2:** SpHb Sensor placement

Devices used for noninvasive hemoglobin evaluation consist of a Masimo Rainbow portable handheld co-oximeter connected to a sensor that measures SpHb, methemoglobin (SpMet), SpO2, pulse rate (PR) and perfusion index (PI). The investigational devices used in this study employ similar material and technology compared to FDA-cleared devices. The investigational devices have undergone risk analysis and safety testing in accordance with applicable safety standards, including electrical safety, current leakage, mechanical safety and biocompatibility testing for patient contacting materials. That risk assessment concluded that the investigational devices do not pose unmitigated risks to operator or subject.

Investigational devices to be used in this study are: INVSENSOR00026 Pulse CO-Oximeter and sensor. The devices used in this study are manufactured per Good Manufacturing Practice (GMP) with traceability of lot or serial numbers and will be labeled as investigational devices, for clinical research only. Final marketed names for the sensor and/or device may change.

The INVSENSOR00026 is a system composed of a handheld Pulse CO-Oximeter and sensor with Rainbow technology similar to already cleared Masimo noninvasive Pulse CO-Oximometers and sensor. The system is intended for spot-check measurements on patients in various care area settings (hospitals, hospital-type facilities, and clinics). The device is a more compact version of already 510(k) cleared Rad-57 and Pronto devices. The Pulse CO-Oximeter device also comes with an upgraded display with touchscreen capabilities. The INVSENSOR00026 Pulse CO-Oximeter and sensor are connected by an accessory patient cable.

The reusable INVSENSOR00026 sensor is intended to measure non-invasive physiological parameters such as SpO2, SpHb, PR, and PI, similar to the existing FDA cleared Masimo rainbow reusable sensors. The sensor has a slimmer and more compact design compared to other Masimo reusable finger sensors. The sensor is intended to be used on patients weighing greater than 3 kg.

## 2 STUDY DEVICE

### 2.1 Description

Investigational Devices:

INVSENSOR00026 Pulse CO-Oximeter and sensor

Laboratory Analysis:

[REDACTED]  
[REDACTED]

[REDACTED]  
[REDACTED]  
[REDACTED]

Safety Equipment (FDA-Cleared)

Blood pressure monitoring system  
Electrocardiogram (ECG)  
Ultrasound system (Bard Site-Rite 8 or equivalent)  
Masimo Pulse Oximeters (Radical-7)  
Pulse oximeter sensors and cables (Masimo SET)  
Masimo Root Patient Monitoring Platform  
Medical-grade oxygen tank and mask  
Crash cart

The PI, delegated study staff and operator(s) will undergo device training per the Directions for Use (DFU) prior to performing any study-related procedures. All training will be documented.

**2.2 Device Accountability**

**2.2.1 Receipt of Study Device**

Masimo may ship or hand-carry devices and sensors to the investigative sites. Upon receipt of the of the study device supplies, an inventory must be performed and the Equipment Shipment Check Form ([REDACTED]) and the device accountability log will be completed for each device and signed by the receiver. It is important that the designated study staff counts and verifies that the shipment contains all the items noted in the shipment inventory. Any damaged or unusable study devices in a given shipment will be documented in the study files. The investigator must notify the study sponsor of any damaged or unusable study devices that were supplied to the investigator's site.

**2.2.2 Use of Study Device**

Use of devices and sensors will be documented on Case Report Forms (CRF) for each subject. Any unused devices must be returned to the Sponsor at the end of the study or before product expiration date.

**2.2.3 Return or Destruction of Study Device**

At the completion of the study, there will be a final reconciliation of study devices. This reconciliation will be logged on the device accountability log. Any discrepancies noted will be investigated, resolved, and documented prior to return or destruction of unused study devices. Devices destroyed on site will only be upon written instruction from the Sponsor and will be documented in the study files.

**2.2.4 Device Deficiency**

Device deficiency is defined as inadequacy of a medical device with respect to its identity, quality, durability, reliability, safety or performance. Device deficiencies include malfunctions, use errors, and inadequate labeling. (ISO 14155:2011 3.15). All Masimo device related deficiencies should be reported to the Sponsor and must be recorded in the CRF in a timely manner. This excludes computer issues. These should be reported to the IRB as required per local requirements. When a Masimo device deficiency is observed, every effort should be made to return the device and its packaging to the Sponsor in a timely manner.

**2.3 Risk/Benefit**

**2.3.1 Benefits:** There will be no direct benefits to the enrolled subjects. Future benefits to subjects might include a reduction in invasive procedures due to the ability to noninvasively measure blood parameters.

- 2.3.2 **Pulse oximeter risks:** The INVSENSOR00026 Pulse CO-Oximeter used during this study are modifications of FDA-cleared devices, are similar in material and technology, and pose no additional risk to the subject.
- 2.3.3 **Sensor risks:** As with all optical sensors, the INVSENSOR00026 sensor investigational device has the risk of thermal burn. The design includes safeguards, and this risk is believed to be low. All patient-contact materials, including the adhesive used in the design of the Masimo Rainbow sensors, have been subjected to biocompatibility tests per ISO 10993-1 and results demonstrate that the materials are non-toxic, non-irritating, and non-sensitizing. The sensors have been subjected to performance, mechanical, and electrical testing and results demonstrate that the sensors meet the requirements for safety and effectiveness for the intended use of the product. The modifications to the sensor are specifically designed so as not to introduce any new risks to the subject, and have been developed pursuant to the design control regulations.
- 2.3.4 **Arterial, and Capillary Blood Draw Risks:** Discomfort is generally associated with needle puncture. The most common complications associated with blood draws and capillary sticks are hematomas or bruising. There is also a possible risk of infection, tendon or tissue damage, damage to the blood vessel and surrounding nerves, and/or loss of feeling in hand and/or arm. Other anticipated adverse events that may occur, include but are not limited to: Vasovagal syncope (passing out/fainting), lightheadedness, feeling flush/ warm, feeling nauseated, throwing up, sudden drop in blood pressure/ sudden increase in blood pressure, sudden drop in heart rate/ sudden increase in heart rate, tingling sensation of face, arms and/or legs, sweating, and/or mouth dryness. These anticipated adverse events are expected to be temporary.
- 2.3.5 **Lidocaine (injection) Risks:** Administration of lidocaine injection may be discomforting and can feel like a slight pinch along with warm/burning sensation. Other anticipated adverse events that may occur, include but are not limited to: flushing or redness of the skin, itching skin, small red or purple spots on the skin, unusually warm skin, bruising, bleeding at the application site, swelling. These adverse events are expected to be temporary. Although not common, it is also possible to have an allergic reaction to injectable lidocaine. Subjects should not take part in this study if they are allergic to lidocaine injection or other types of numbing medicine, or if they have a heart rhythm disorder such as Wolff-Parkinson-White Syndrome or Stokes-Adams syndrome. Subjects are instructed to tell the study staff right away if they experience hives; difficulty breathing; swelling of the face, lips, tongue or throat.
- 2.3.6 **Topical Anesthetic (such as Pain Ease):** Topical anesthetic which is used to prevent pain by cooling the skin. Although unlikely, the anticipated adverse events that may occur, include but are not limited to: changes in skin color (i.e. flushing or redness of the skin), delayed wound healing, rash, itching and swelling. These adverse events are expected to be temporary.

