#### 4.6 Inclusion Criteria

- 18 years of age or older
- Subject has given written informed consent to participate in the study

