#### 4.7 Exclusion Criteria

- (\*) Pregnant or positive human chorionic gonadotropin (hCG) test
- (\*) Any severe coagulopathy, chronic bleeding disorders (i.e., hemophilia) or recent thrombolysis
- (\*) Hemoglobinopathies and synthesis disorders (i.e., sickle cell, thalassemias, etc.)
- (\*) Subjects who are currently taking anticoagulant medication
- (\*) Subjects with allergies to lidocaine, Pain Ease, latex, adhesives, or plastic
- (\*) Subjects with skin abnormalities at the planned application sites that may interfere with sensor application, per directions-for-use (DFU) or trans-illumination of the site, such as psoriasis, eczema, angioma, burns, scar tissue, substantial skin breakdown, nail polish, acrylic nails, infections, abnormalities, etc.
- (\*) Subjects unlikely to be able to refrain from excessive motion during data collection. Excessive motion includes postural changes, making hand gestures, involuntary muscular movements, etc.

- (\*) Subjects with elevated blood pressure, skin or wrist abnormalities that may interfere with an arterial blood draw as determined by investigator or research medical staff.
- (\*) Subjects who intend on participating in heavy lifting, repetitive movement of their wrist (including riding a motorcycle) or exercise (working out, riding a bike, etc.), or any activity that will put additional stress on the wrist within 24 hours following a study involving an arterial blood draw
- Subjects deemed not suitable for the study at the discretion of the investigator or research medical staff

Note: (\*) May be self-reported by subject

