## **5 STUDY PROCEDURES**

### **5.1 Subject Recruitment and Screening**

Subjects may be recruited for the study from the physician's clinical practice or by advertisement. Information to be disseminated to subjects and any advertisements will be approved by the IRB. Once a potential subject sees the recruitment material (i.e. advertisement) they can contact the clinical site to schedule an appointment. Potential subjects may also be identified by review of the site's appointment schedule for subjects that may be eligible for the study. Potential subjects may be contacted by phone by study staff using the IRB-approved phone recruitment script.

Subjects will be screened to determine their potential eligibility and interest in a study. Subjects' potential eligibility can be evaluated during their routine intake at the clinic when health history and other information are gathered for their pre-existing appointment with the clinic, or during the recruitment phone call. All subjects screened will be documented on the Screening and Enrollment log.

Subjects are considered enrolled in the study once the subject has signed and dated the informed consent. Subjects must also meet all of the inclusion criteria and none of the exclusion criteria. If the subject signs the Informed Consent form and is identified later as failing to meet all eligibility criteria, the subject will be classified as a screen failure. Upon determination that the subject does not qualify for enrollment, the reason for the subject's screen failure status will be documented on a Screening and Enrollment Log, in order to minimize bias. In case a subject leaves the study prematurely, another volunteer may be recruited.

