### **9.3 Case Report Forms**

The Site shall capture study data in the CRFs for each subject enrolled. The CRFs will be completed and initial and dated by the PI or delegated personnel. This also applies to those subjects who fail to complete the study. If a subject withdraws from the study, the reason must be noted on the CRF. Case report forms are to be completed on an ongoing basis. CRF entries and corrections will only be performed by study site staff, authorized by the investigator. Entries and corrections to the CRF will be made following Good Documentation Practices.

The CRF will include the following information, including but not limited to: inclusion/exclusion criteria, whether patient consent obtained before start of study, demographic information, device readings, and if occurrence of any adverse event, protocol deviation, and device deficiencies, etc. The CRFs will be signed by the PI to attest that the data is complete and accurate and forward a copy to Masimo.

CRF entries will be verified by study monitor and any errors or inconsistencies will be queried to the site on an ongoing basis. Any changes will be made directly on the paper CRFs and re-verified. Query resolution will be assessed and confirmed by study monitor during site visit. The monitor or study manager will collect original completed and signed CRFs at the end of the study. A copy of the completed and signed CRFs will remain on site

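### Section 2.3.5 says subjects with a heart rhythm disorder should not take part, but no specific exclusion criterion in section 4.7 carries that restriction

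*Combined protocol and SAP*

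**What the plan says.** The sentence in section 2.3.5 (lidocaine injection risks) begins "Subjects should not take part in this study if they are allergic to lidocaine injection or other types of numbing medicine" and continues "or if they have a heart rhythm disorder such as Wolff-Parkinson-White Syndrome or Stokes-Adams syndrome". It gives two grounds, allergy and heart rhythm disorder, and both bear on taking part in the study as a whole, not only on receiving the injection.

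Section 4.7 carries the lidocaine-allergy ground in one item: "Subjects with allergies to lidocaine, Pain Ease, latex, adhesives, or plastic". It ends with a general item: "Subjects deemed not suitable for the study at the discretion of the investigator or research medical staff". Section 4.6 has two inclusion criteria, an age limit and "Subject has given written informed consent to participate in the study".

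Section 5.1 applies these lists to enrolment: "Subjects must also meet all of the inclusion criteria and none of the exclusion criteria". Section 9.3 carries them into data capture: "The CRF will include the following information, including but not limited to: inclusion/exclusion criteria".

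Under section 5.3.4.5, lidocaine injection, a topical anesthetic or both may be used for an arterial draw, and the subject may decline.

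**The concern.** A restriction on who may take part is stated in the risk section but is not a specific item in the list that site staff work from. One half of the sentence reached the list and the other did not, which looks like an incomplete carry-over. Nothing visible suggests that the restriction was meant to be limited or withdrawn.

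What is at stake is subject safety and uniform eligibility across sites. In a multi-center study, one site may act on 2.3.5 while another works only from 4.7. They could then differ on whether enrolling such a subject is acceptable, a screen failure or a deviation.

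The case is not far-fetched on the protocol's own text. Section 4.4 recruits both healthy and unwell adults with varied comorbidities, section 6.1.5 wants data from several health conditions, and section 1.1 gives arrhythmia as an example of the heart problems that untreated anemia can cause. None of these says that subjects with rhythm disorders are sought; together they only show that such subjects could present.

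**Working it through.** There is no figure in the plan to reproduce and no arithmetic beyond counting. The check sets the restriction beside each place where eligibility is defined, then follows how those places are used.

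**Step 1: where the restriction could appear**

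| Place | Items | Naming a heart rhythm disorder |
|---|---|---|
| 4.6 inclusion criteria | 2 (age, consent) | 0 of 2 |
| 4.7 specific exclusions (all starred) | 9 | 0 of 9 |
| 4.7 discretionary exclusion | 1 | names no condition |
| 5.3.1.1 to 5.3.1.4 eligibility steps | 4, of which 3 can end in removal | 0 of 4 |

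Section 4.7 therefore has 9 + 1 = 10 items. The only cardiovascular sign among them is elevated blood pressure, in an item about interference with the arterial draw. No redaction is visible in 4.6 or 4.7.

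**Step 2: how much of the 2.3.5 sentence was carried over**

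The lidocaine-allergy ground has its own item in 4.7. The rhythm-disorder ground has none. That is one of the sentence's two grounds.

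**Step 3: whether 4.7 is the only home for such conditions**

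It is not. Section 5.3.1 adds two grounds for removal that 4.7 does not name: declining the pregnancy test (5.3.1.2) and a negative Allen's test (5.3.1.3). Each has an explicit step with a stated consequence. No visible step does the same for a heart rhythm disorder.

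**Step 4: where the lists are used**

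- Section 5.1 ties eligibility and screen failure to the criteria.
- Section 5.2.1 uses them to define who is approached for consent.
- Section 5.3.1.1 ties removal after the questionnaire to them.
- Section 9.3 has the CRF record them.

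**Step 5: the path that results**

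A subject with a rhythm disorder and no other listed condition meets both inclusion criteria and none of the 9 specific exclusions. Unless staff act on 2.3.5 or use the discretionary item, the subject can be enrolled. Lidocaine could then be offered only if an arterial draw is done. Section 4.1 makes the arterial sample the reference, but 4.5 and 5.3.4.2 allow that not every subject has one, and 5.3.4.5 lets the subject refuse the anesthetic.

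**Step 6: how many subjects**

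Section 4.5 caps enrolment at 300. The documents give no prevalence of rhythm disorders, no count of arterial draws and no rate of lidocaine acceptance, so the number affected cannot be computed.

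**The case against.** The strongest reply is that the sections do not give opposite instructions. Nothing in 4.7 admits a subject with a rhythm disorder, and an investigator who follows both sections keeps such a subject out. Several provisions support that:

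- Sections 1 and 12 bind the investigator to the whole protocol, 2.3.5 included.
- Section 10 has the monitor verify adherence to the clinical investigational plan as well as to the listed criteria.
- Section 7.4 requires deviations to be recorded, and unapproved ones that may affect subject safety to be reported within 5 working days.
- Health history may be taken at clinic intake (5.1). A questionnaire is discussed with medical staff, and medical history is recorded (5.3.1).
- ECG is among the monitors used during the procedure, with stopping on distress (5.3.2.1).
- The discretionary exclusion is available.

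Much of this stands. A reader might infer that a monitor who found a rhythm disorder in the history would have nothing to check it against. The documents do not support that, because 2.3.5 is part of the plan whose adherence the monitor verifies. A reader might also infer that sites do not screen for the condition. That cannot be shown either: the questionnaire, CRF form and consent pages are not visible, and parts of 5.3, 5.3.1.4, 5.3.2 and 5.3.3 are redacted.

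What does not stand is the step from safeguards to agreement. The discretionary item permits exclusion but does not require it, whereas 2.3.5 does not leave the matter to discretion. ECG during the procedure is monitoring, not an eligibility test. The option to decline lidocaine does not remove the restriction, because 2.3.5 concerns taking part and is not conditioned on accepting the injection. A general duty to follow the protocol makes 2.3.5 binding, but it does not put the restriction into the lists used for enrolment and the CRF.

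**Conclusion.** The mismatch is real and should be fixed. Section 2.3.5 states a ground for not taking part that is absent from all 9 specific exclusions, both inclusion criteria and all 4 visible eligibility steps, although the lidocaine-allergy ground in the same sentence is listed.

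The finding is confined to the visible text. It rests on 4.6 and 4.7 being complete as shown, and on no redacted procedure text carrying the restriction. I have not seen the text between 4.2 and 4.4, but it lies outside the two criteria lists. Confidence is high that the list entry is missing. No claim is made that screening in practice fails, that any given number of subjects is exposed, or that the restriction cannot be audited.

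The broader allergy wording in 2.3.5, set against the named products in 4.7, might be read as a second gap. It is only a difference of wording, since 4.7 names both anesthetic products that the protocol names.

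The accuracy analysis in 4.2 and 6.2 is not affected.

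**What to change.** Reconcile sections 2.3.5 and 4.7 so that the conditions said to preclude participation and the conditions screened against are the same. The change could fall in either section; the sponsor and investigator decide the clinical content. Then check the Health Assessment Questionnaire and the eligibility part of the CRF against the reconciled text, and correct them only if they differ.

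The cost is a short amendment, agreed and signed by the investigator and sponsor and approved by the IRB under section 11.4, plus a review of the two forms. Depending on how the sections are reconciled, a few otherwise eligible subjects may be lost, or none; the documents give no basis for a number.
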